10.2 Causality Assessment

For all AEs, the Investigator must provide an assessment of causal relationship to study drug. Causal relationship must be assessed according to the following scale:

- | | |
|--------------------------|---|
| Related: | Reasonable temporal relation to study drug administration AND cannot be reasonably explained by other factors (eg, the patient's clinical state, concomitant therapy, and/or other interventions). |
| Possibly Related: | Relationship to study drug cannot be ruled out. |
| Not Related: | Data are available to identify a clear alternative cause for the reaction (eg, positive test for viral antigen in a case of suspected drug-induced hepatitis, hemorrhage due to mechanical injury). |

10.3 Severity Assessment

The Investigator will provide an assessment of the severity of each AE. *Severity*, which is a description of the intensity of manifestation of the AE, is distinct from *seriousness*, which implies a patient outcome or AE-required treatment measure associated with a threat to life or functionality. Severity of AEs will be graded according to CTCAE criteria, version 4.

11.0 Statistical Methods and Determination of Sample Size

The overall study objectives are broad: (1) to assess breast cancer survivors with chronic pain for the presence and degree of pain centralization and (2) to identify predictors of response to the predominantly centrally-acting analgesic duloxetine in breast cancer survivors with chronic treatment-emergent pain. In order to examine these objectives, as noted in section 9 of the protocol, the primary outcome measure is the Brief Pain Inventory and the secondary outcome measures are objective measures of pain sensitivity and other patient-reported outcomes questionnaires. These measures are used to assess patients with chronic pain who are treated with duloxetine, in order to assess change in these outcomes with therapy, and also to assess control patients without chronic pain in order to define differences in these measures between the two cohorts and to facilitate interpretation of the change in these scores in duloxetine-treated patients. These results will be used to explore centralized pain in this patient population including identification of predictors of response to duloxetine.

Primary outcome:

Change in worst pain from baseline to week 5 with 5 weeks of duloxetine therapy, using the worst pain score from the BPI

Secondary outcomes:

- Change in average pain from baseline to week 5 with 5 weeks of duloxetine therapy, using the average pain score from the BPI
- Change in pain interference from baseline to week 5 with 5 weeks of duloxetine therapy, using the pain interference score from the BPI

- c. Change in number of sites of pain from baseline to week 5 with 5 weeks of duloxetine therapy, using the Michigan Body Map
- d. Change in Fibromyalgia Severity Score from baseline to week 5 with 5 weeks of duloxetine therapy, using the Michigan Body Map and Symptom Severity Scale
- e. Change in Neuropathic Pain from baseline to week 5 with 5 weeks of duloxetine therapy, using the PainDETECT
- f. Change in Neuropathy from baseline to week 5 with 5 weeks of duloxetine therapy, using the FACT/GOG-NTX
- g. Change in Fatigue from baseline to week 5 with 5 weeks of duloxetine therapy, using the PROMIS Fatigue 7a
- h. Change in Sleep Disturbance from baseline to week 5 with 5 weeks of duloxetine therapy, using the PROMIS Sleep Disturbance 8b
- i. Change in Physical Function from baseline to week 5 with 5 weeks of duloxetine therapy, using the PROMIS Physical Function 10a
- j. Change in Anxiety from baseline to week 5 with 5 weeks of duloxetine therapy, using the Hospital Anxiety and Depression Scale
- k. Change in Depression from baseline to week 5 with 5 weeks of duloxetine therapy, using the Hospital Anxiety and Depression Scale
- l. Change in the 5 components of Cognitive Difficulties from baseline to week 5 with 5 weeks of duloxetine therapy, using the Multiple Ability Self-Report Questionnaire
- m. Change in pain sensitivity from baseline to week 5 with 5 weeks of duloxetine therapy, using the Pain50 assessed using quantitative sensory testing
- n. Change in CPM from baseline to week 5 with 5 weeks of duloxetine therapy, using quantitative sensory testing

Exploratory analyses:

Assessment of Centralized Pain. Centralized pain will be assessed within the unsupervised classification paradigm. Measures of pain centralization (pain severity (BPI) and distribution (Michigan Body Map)), symptom severity scale, neuropathic pain (PainDETECT), functional status (PROMIS), anxiety and depression (HADS), cognitive measures (MASQ), and experimental pain (QST)) will be treated as a multivariate phenotype informing about the latent centrality status of the subject. Demographic (e.g., age, BMI) and clinical (treatment “bin”) variables will be added as covariates. We will assume that the hypothesized centrality status is expressed by a latent variable specific to the subject, a random effect.

This variable will be used as an effect modifier in a regression model linking the primary response of pain severity and other response variables with the phenotype variables. The resultant mixture of regression models where the latent centrality variable will be shared by all regression models within the subject will be fit by the EM algorithm with iterative imputation of the latent centrality status. Regression models for each response variable will be of the generalized linear models (GLM) family. The data will have ample information to bear on the distribution of patients over the latent classes as the model will borrow strength from all contributing GLMs. The model will be refined in layers by adding response and predictor variables deemed informative of the latent centrality. The performance of the model will be measured by the Akaike Information Criterion (AIC). A threshold of 2 per 1 degree of freedom will be applied to AIC differences between models as a measure of significant difference between models. The model showing the highest AIC will be selected as the best model for subsequent analysis and prediction. The latent centrality status will be predicted for each subject by a Bayesian argument using the best model. Continuous, ordered categorical and binary latent centrality status will be explored in search for the model that provides the best explanation for the heterogeneity of pain responses in the breast cancer survivors.

As an illustration of the method we fitted a binary centrality status (central vs. non-central) model (a mixture of two different latent linear regression models specific for the centrality class) to cross-sectional pain severity data on 199 breast cancer patients from an unpublished cross-sectional study we conducted on breast cancer survivors 1-3 years following diagnosis. PainDETECT, age, BMI, HADS depression and anxiety, sleep disturbance, fatigue, Perceived Stress Scale, and treatment bin (listed in Figure 4) were used as explanatory phenotype variables. The model resulted in identification of two clusters (cluster 1: 64% of patients; cluster 2: 36%) of breast cancer patients defined by dissimilar regression relationships between pain and phenotype and clinical variables. Cluster 2 is characterized by persistently higher levels of pain (Figure 5). Age, BMI and fatigue are significant variables in Cluster 1 while neuropathic pain and depression mark Cluster 2 regression. While in the data analysis we will favor continuous characterization of centrality, this binary model is used as a source of information for the power analysis below. Using the AIC criterion, the two-cluster model is significantly better than the homogeneous patient population (one regression, no latent heterogeneity explained by centrality). We note that treatment was not significant ($p=0.39$), in line with our hypothesis of common pain mechanism regardless of the type of insult.

Analysis. The planned sample size for Aim 1 is 132 (84 cases and 48 controls). For Aim 2, latent dichotomous pain centrality status will be hypothesized and regressed on explanatory variables including the ones involved in the CNS pain regulation. We will assume that the causality of the effect of the centrality block of variables on the Duloxetine (DLX) treatment outcome will follow through the centrality status. In addition to the random effect representing the interaction between the drug effect and the

[figure not shown]

Fig. 5. Clustering of 199 BCS using a mixture of 2 (pain ~ phenotype + treatment + demographics) regression models. Red high pain latent cluster is loosely identified with predicted centralized pain classification, and the blue cluster with non-centralized. Note that none of the phenotype variables taken alone serves as a particularly good surrogate for the classification, and the mixture approach that borrows strength across various phenotypes is essential.

central status, subject specific random intercept will be introduced to model correlation due to repeated measurements. A generalized linear mixed model will be used with the two response variables (self-report pain questionnaires and experimental pain testing scores). The form of the link function and variable transformations will be determined based on the data using AIC criteria. A full likelihood model-based approach will be used to fit the model. Hypotheses will be tested by the likelihood ratio test. A clinically relevant response is defined as 50% reduction in pain within the patient. The following effects are hypothesized based on our pilot studies: Central patients will constitute approximately 30% of the breast cancer population; 10% of non-central patients are hypothesized to show clinically relevant improvement under DLX while the rate of at least 70% is hypothesized in the central group. Overall, this leads to the expected 28% response rate. Placebo effects in this kind of studies are expected not to exceed 3%. Conservatively we would be looking to detect improvement over twice the expected placebo rate (6%). Using a two-sided test for the proportion of improvement vs. 6% at $\alpha=0.05$ we will have the power of 81% with 21 patients in each "bin" (total of 84 patients).

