3.0 STUDY OBJECTIVES

- 1) To assess breast cancer survivors with chronic pain for the presence and degree of pain centralization
- (2) To identify predictors of response to the primarily centrally-acting analgesic duloxetine in breast cancer survivors with chronic treatment-emergent pain.

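### The only method for finding predictors of duloxetine response selects its model by AIC from an open list without internal validation, so noise variables may well be selected and prediction overstated

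*Combined protocol and SAP*

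**What the plan says.** Section 3.0 gives the second objective as: "To identify predictors of response to the primarily centrally-acting analgesic duloxetine in breast cancer survivors with chronic treatment-emergent pain". The Synopsis calls both objectives primary. The primary and secondary outcomes listed in Section 11.0 are all changes from baseline to week 5, and none of them identifies a predictor. The method for the second objective stands further down, under the exploratory analyses.

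That text has two parts.

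- **Assessment of centralized pain.** The questionnaire and sensory-testing battery is treated as a multivariate expression of a latent centrality status, with age, BMI and treatment bin as covariates. The mixture is fitted by EM. On model building: "The model will be refined in layers by adding response and predictor variables deemed informative of the latent centrality". On the latent variable: "Continuous, ordered categorical and binary latent centrality status will be explored in search for the model". AIC is the only performance measure, with a threshold of 2 per degree of freedom on AIC differences. The selected model is carried forward into later analysis and prediction. On numbers: "The planned sample size for Aim 1 is 132 (84 cases and 48 controls").
- **Aim 2.** A dichotomous latent status is posited, and the centrality variables are assumed to act on treatment outcome through it. A mixed model is fitted to self-reported and experimental pain scores. Link and transformations are chosen on the data by AIC, and hypotheses are tested by likelihood ratio. The paragraph just before this says that a continuous form of centrality will be favored.

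Section 11.0 mentions no bootstrap, cross-validation, hold-out sample, shrinkage or multiplicity control.

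**The concern.** A model whose variables, latent form, link and transformations are all chosen for their fit will look better on the data that chose it than on new patients. Likelihood ratio tests run afterwards on the same data do not hold their nominal level, because their reference distribution takes no account of the search. The exploratory label does not settle the matter, since nothing else in the plan addresses a primary objective.

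The first part has 132 subjects, but the 48 controls are assessed once and receive no duloxetine (Sections 5.1 and 8.2). Only the 84 cases carry information on response.

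At stake is whether a reader of the results can tell real predictors from chance ones. Section 2.0 hopes that the findings could lead to individualized therapy. In-sample fit alone would be a weak basis for that.

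**Working it through.** **1. The plan's own figures.** Inputs, all from Section 11.0: "Central patients will constitute approximately 30% of the breast cancer population"; "10% of non-central patients are hypothesized to show clinically relevant improvement under DLX"; at least 70% in the central group; null rate 6%; two-sided 0.05; 21 patients per bin.

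- Overall rate: 0.30 × 0.70 + 0.70 × 0.10 = 0.28. This agrees with the plan: "Overall, this leads to the expected 28% response rate".
- Power by the arcsine approximation: Φ(h√21 − 1.96) with h = 2(arcsin√0.28 − arcsin√0.06) gives 81.1%, against 81% stated.
- Expected responders: 84 × 0.28 = 23.5.

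The calculation reproduces. It sizes a response proportion within a bin and says nothing about finding predictors.

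**2. Number of candidates (an assumption, because the list is open).** Counting the scores named in Section 11.0: worst pain, average pain, interference, number of sites, fibromyalgia score, PainDETECT, FACT/GOG-NTX, 3 PROMIS, 2 HADS, 5 MASQ, Pain50 and CPM make 19. Age, BMI and bin (3 df) would bring this to 24 df. The range tested is 9 to 24.

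**3. What the AIC rule means per variable.** With AIC = 2k − 2 log L, adding one parameter lowers AIC by LR − 2.

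- Literal threshold (drop greater than 2): LR > 4, chance under the null 0.0455.
- Looser reading (any drop): LR > 2, chance under the null 0.157.

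**4. Chance that at least one of m independent noise variables passes at first entry, 1 − (1 − a)^m.**

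- m = 19: 1 − 0.9545^19 = 59% (LR > 4); 1 − 0.843^19 = 96% (LR > 2).
- m = 9: 34% and 79%.
- m = 24: 67% and 98%.

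**5. Null simulation of forward selection.** n = 84, no true predictor, candidate correlation 0 or 0.4. There were 400 data sets per setting for the binary outcome (response probability 0.28) and 500 for the continuous one. Entries are the share of data sets with at least one false predictor; each range spans the two correlations.

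| Outcome | Candidates | LR > 4 | LR > 2 |
|---|---|---|---|
| 50% responder | 9 | 28–33% | 72–78% |
| 50% responder | 19 | 48–60% | 92–95% |
| 50% responder | 24 | 59–69% | 93–99% |
| Continuous score | 9 | 28–33% | 76–82% |
| Continuous score | 19 | 47–63% | 89–97% |
| Continuous score | 24 | 50–68% | 92–98% |

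A separate run with a continuous outcome and correlation 0.4 gave 45% (LR > 4) and 86% (LR > 2) with 19 candidates, and 31% (LR > 4) with 9. Together with the table, 19 candidates give 45–63% and 86–97%.

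**6. Size of the optimism, 19 candidates.** For a continuous score the mean apparent R² was 0.05–0.07 (LR > 4) and 0.13–0.14 (LR > 2), with a true value of zero. For the responder outcome the mean apparent AUC was 0.60–0.62 and 0.71–0.72, with a true value of 0.50.

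**7. Does the remedy work?** Selection was repeated inside each bootstrap sample (40 noise data sets, 30 resamples each, 19 candidates, correlation 0.4). Mean AUC fell from 0.68 to 0.50 under LR > 2, and from 0.57 to 0.44 under LR > 4. The second is a slight over-correction, and both carry Monte Carlo noise. The spurious discrimination is removed.

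**The case against.** The strongest reply is that the layered building belongs to another model. Variables enter there because they inform centrality, in an unsupervised analysis, and the Aim 2 text names AIC only for link and transformations. A reader might infer that responder predictors are picked directly by layered AIC; the documents do not say so. What remains is the link between the two parts. The latent status modifies the regression for pain severity, the winning model is carried into prediction, and Aim 2 routes the effect of the centrality variables through that status. The search therefore reaches the second objective indirectly.

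A second tempting reading is that about 24 responders face about 20 candidates, roughly one event each. The plan does define a responder: "A clinically relevant response is defined as 50% reduction in pain within the patient". But the modelled outcomes are pain scores, so that ratio binds only if the responder is what is analyzed. The continuous rows of the table show that the problem does not depend on it.

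Third, the plan promises no AUC, so the AUC figures only illustrate optimism. Fourth, forward selection is simpler than a shared-latent mixture. Finally, a real signal may be present. If the 70% versus 10% contrast held and status were known without error, sensitivity would be 0.21/0.28 = 0.75, specificity 0.63/0.72 = 0.875 and AUC (0.75 + 0.875)/2 = 0.81. True and false predictors could then appear side by side, and the plan as written could not separate them.

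**Conclusion.** The concern holds in a limited form, and acting on it is a cheap improvement. The only method for a primary objective combines an open variable list, a search over latent forms and AIC-driven choices with later tests, and has no internal validation. With 19 assumed candidates, selection of at least one noise variable is about as likely as not under the literal threshold (45–63%) and very likely under the looser one (86–97%). A battery of 9 still gives 28–33% and 72–82%.

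A reader might go further and conclude that false predictors are bound to appear. The literal threshold does not support that; they may well appear.

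The figures rest on the candidate count, on correlations of 0 to 0.4, and on forward selection as a stand-in. The search over three latent forms and over links is not modelled. The Monte Carlo standard error is at most √(0.5 × 0.5/400) = 2.5 percentage points for the 400-data-set entries and smaller for the 500-data-set entries.

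**What to change.** Keep the latent-class approach. The Figure 5 caption treats the mixture as essential, and replacing it with ridge or lasso would be a debatable trade-off that this concern does not require. In Section 11.0:

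- Close the candidate list, and name one primary form of centrality for Aim 2. The text now points to both dichotomous and continuous.
- State whether the AIC threshold means LR > 4 or LR > 2. Also state the sign convention, since the text selects the highest AIC whereas under the usual definition the lowest is best.
- Repeat the whole process (variables, latent form, link, transformations) in bootstrap samples of patients.
- Report optimism-corrected prediction of pain change and of the 50% response, with how often each variable is selected.
- Give no unadjusted p-values for selected variables, and label the predictors hypothesis-generating.

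The cost is SAP wording, computing time and lower reported predictive performance; no extra patients or visits are needed. Validation exposes optimism but adds no information to 84 patients, which is why the hypothesis-generating label is still needed.

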9.0 Outcome Measures

9.1 Primary Outcome Assessment

9.1.1 Brief Pain Inventory

The Brief Pain Inventory (BPI) is a 17-item patient self-rating scale that assessed sensory and reactive components of pain.⁶⁹ For sensory components, it addresses severity, location, chronicity, and degree of relief due to therapy. For reactive components, it assesses depression, suffering, and perceived availability of relief. Reliability has been demonstrated over short intervals using test retest item correlation; worst pain, $r=0.93$, usual pain, $r=0.78$, pain now $r=0.59$. It has been validated in patients with both cancer and non-cancer pain.^{76,77} Ratings of pain interference with various activities increased as ratings of pain severity were higher. The proportion of patients receiving opioid analgesics also increased with increased severity rating.

The BPI uses 0 to 10 numeric rating scales for item rating because of its simplicity and lack of ambiguity. Since pain can be variable over a day, the BPI asks patients to rate their pain at the time of completing the questionnaire, and also at its worst, least, and average over the previous 24 hours. The primary endpoint for this clinical trial will be based on the 24-hour average pain as reported on the BPI. The ratings can be combined to give a composite index of pain severity. Also, using numeric 0 to 10 scales, with 0 being “no interference” and 10 being “interferes completely”, the BPI asks for ratings of the degree to which pain interferes with mood, walking and other physical activity, works, social activity, relations with others, and sleep. The mean of these scores can be used as a pain interference score.

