9.2 Secondary Outcome Assessments

9.2.1 Pressure Pain Threshold

Most QST will be performed using the MAST System. The MAST System is a wireless QST platform featuring a control computer, a touch screen for patient feedback, and an automated pressure actuator. Forces are delivered by a 1-cm² conformal-rubber probe attached to a cylindrical transducer driven by a miniature servo-motor and housed within a polyurethane case that is held comfortably in either hand. Load-cells measure each applied force while a closed-looped control system monitors and adjusts motor output ensuring accurate pressure delivery. All subjects will undergo bilateral pressure pain testing (PPT) at the thumbnail.⁵² The thumbnail was chosen as a neutral, pain-free site remote from the area of surgery. Increased pain sensitivity at the thumbnail (i.e., secondary hyperalgesia) suggests a state of widespread hyperalgesia that may be indicative of centralized pain.^{47,51,54,108} Subjects will undergo testing bilaterally to determine the effect, if any, of prior breast and axillary surgery on thumbnail pressure sensitivity. Testing will be counter-balanced between left and right thumbs. The MAST System will first deliver an ascending series of pressures (5-s duration; 4 kg/cm²/s) at 25-s intervals, beginning at 0.25 kg/cm² and increasing in 0.25 – 0.50 kg/cm² intervals up to tolerance or to a maximum of 10 kg/cm² to the thumbnail. Pain intensity will be rated after each stimulus on a 0-100 numerical rating scale (NRS), with “0” representing “no pain” and “100” representing “extreme pain”. Patient responses obtained in the ascending series will be used to compute a set of 5-7 stimuli between that patient’s threshold and tolerance. These stimuli will then be delivered and rated 3 times each (5-s duration; 25-s inter-stimulus interval) in randomized order. These ratings will be used to compute a psychophysical function of each subject’s pain sensitivity with pressure intensity and response magnitude represented on the x- and y-

axes, respectively. These curves will be used to compare single subject and group changes in pain sensitivity longitudinally throughout the project. Pressure pain threshold and tolerance levels will also be calculated for each subject at each thumbnail.

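### Section 11.0 picks the exploratory centrality model by the highest AIC; under the standard definition lower is better, so the rule as written is reversed

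*Combined protocol and SAP*

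**What the plan says.** Section 11.0, under the exploratory assessment of centralized pain, describes a latent-variable mixture of regressions fitted by EM, with AIC as the measure of model performance. Four statements matter here.

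- Building the model: "The model will be refined in layers by adding response and predictor variables deemed informative of the latent centrality".
- Judging a difference: "A threshold of 2 per 1 degree of freedom will be applied to AIC differences between models". No direction is given.
- Choosing the model: "The model showing the highest AIC will be selected as the best model for subsequent analysis and prediction".
- Using the choice: "The latent centrality status will be predicted for each subject by a Bayesian argument using the best model".

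The same section illustrates the method on 199 patients from a separate cross-sectional study and reports: "Using the AIC criterion, the two-cluster model is significantly better than the homogeneous patient population". It gives no AIC values.

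AIC appears once more, in the Aim 2 analysis text of Section 11.0, where it guides the choice of link and of any transformation of variables. No direction is given there either. Nowhere do the documents define AIC or its sign.

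**The concern.** As usually defined, AIC is a penalized lack-of-fit measure, and the preferred model has the smallest value. A rule that takes the largest value prefers poorer fit for the number of parameters used. The chosen model is not background: it supplies each subject's predicted centrality status. Section 3.0 gives as objective 1: "To assess breast cancer survivors with chronic pain for the presence and degree of pain centralization". If the sentence were followed literally, the classification serving that objective would come from the wrong end of the ranking, and it would tend to discard the latent heterogeneity that the analysis is meant to find.

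Two related gaps lie beside it. The layered refinement adds response variables as well as predictors, and AIC values for different sets of responses are not comparable. The Aim 2 text may also compare models across transformations, which raises the same problem if a response is what is transformed.

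**Working it through.** **Plan figures.** The documents state no AIC value, so there is none to reproduce. The one power figure in Section 11.0 can be reproduced, and doing so shows that AIC plays no part in it. The inputs are a response rate of 28% (0.30 × 0.70 + 0.70 × 0.10), a reference rate of 6%, two-sided alpha 0.05 and 21 patients per bin. With the arcsine approximation:

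2 × (asin√0.28 - asin√0.06) × √21 - 1.96 = 2 × (0.5576 - 0.2475) × 4.583 - 1.96 = 0.882, and Φ(0.882) = 0.811, matching the stated 81%.

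**Direction of the rule.** Take two nested models for the same subjects and responses, the larger with q more parameters, and let LR be twice the gain in maximized log-likelihood. With AIC = 2k - 2logL,

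change in AIC = 2q - LR.

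The larger model is supported when LR > 2q, and its AIC is then lower. The literal rule picks it only when LR < 2q, that is, when AIC does not support the added terms. The ranking is exactly inverted.

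**Against the plan's illustration.** The two-cluster model was judged better than one regression by AIC. On the standard scale its AIC must therefore have been the lower of the two. Applied to that same pair, the highest-value rule selects the single regression. The illustration and the selection sentence agree only if AIC is defined with the opposite sign.

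**The reversed convention.** 2logL - 2k is minus the standard AIC, so its highest value and the lowest standard AIC always identify the same model. The threshold of 2 per degree of freedom has the same size on either scale. The text would be consistent under this convention, but it does not state it.

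**The threshold read as a reduction.** Requiring AIC to fall by more than 2 for one added predictor means 2 - LR < -2, so LR > 4. The chi-square tail on 1 degree of freedom beyond 4 is 0.0455, or p = 0.046. Read this way, the threshold is a sensible criterion for one added predictor. That p-value does not carry over to the number of latent classes, where the usual chi-square reference does not apply.

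**Layers that add a response.** Each new response adds its own term to the log-likelihood. For a Normal response with residual SD s and n subjects, the addition to -2logL is n(ln(2πs²) + 1). Multiplying the units by c changes it by 2n ln c. The size, and even the sign, of the AIC change therefore depends on the measurement scale. The plan's scales differ: Section 9.1.1 rates BPI items from 0 to 10, and Section 9.2.1 rates evoked pain from 0 to 100. The plan gives no residual SD, so no figure is attached to this.

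**Transformed responses in Aim 2.** If a response y is modelled as g(y), the log-likelihood on the original scale is that of g(y) plus the sum of ln|g′(y)| over observations. Without this Jacobian term, AIC values for y and g(y) cannot be compared.

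**The case against.** The strongest reply is that this is a one-word slip in an analysis labelled exploratory. The authors' own illustration reads AIC sensibly, and any statistician running the model would take the smallest standard AIC. Objective 1 does not rest on this model alone either, because Section 11.0 also sets out comparisons of the measures between cases and controls. All of this stands and settles the severity. It does not remove the point: the sentence is an operative selection rule, and nothing else in the documents supplies its sign.

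A reader might also infer that taking the highest AIC cannot operate together with the threshold, since adding terms can raise standard AIC by at most 2 per degree of freedom. The documents do not support that. The threshold applies to differences in either direction, and the smaller model's AIC can exceed the larger one's by far more than 2. As an illustration, assume an ordinary regression and one added predictor with partial correlation r, so that LR ≈ -n ln(1 - r²). For r = 0.2, 0.3 and 0.4, the smaller model's AIC is higher by about 3.4, 10.4 and 21.0 at n = 132, and by 1.4, 5.9 and 12.6 at n = 84. The plan gives no such correlations. The literal rule works with the threshold; it simply tends to choose the smaller model.

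On the layers, it is fair to say that the plan does not state that AIC will be compared across different sets of responses. It describes adding responses and judging models by AIC in the same paragraph, which implies such comparisons without prescribing them. The restriction is therefore a clarification.

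**Conclusion.** The selection rule is reversed as written under the standard definition of AIC, and the documents state no other definition. A wording slip is the likely explanation. Severity is minor.

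The reach is narrow: the exploratory centrality model and the status predicted from it. In Aim 2, AIC guides only modelling choices and no direction is stated, so the text there is incomplete but not reversed; its hypotheses are tested by likelihood ratio.

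A reader might infer that the trial's main results or its size are compromised. They are not. The primary outcome, secondary outcomes a to n, the planned 84 cases and the 81% power make no use of AIC. Nor do the documents show that any analysis has been run in the wrong direction; the illustration suggests the opposite.

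The conclusion assumes that AIC carries its standard sign. If 2logL - 2k was meant, the choice of model is right and only the missing formula needs supplying. The need to compare like with like remains under either sign.

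**What to change.** In Section 11.0, under the assessment of centralized pain:

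1. Replace the selection sentence with: *The model with the lowest AIC (AIC = 2k - 2logL) will be selected.* If 2logL - 2k is intended, keep the present direction and state that formula.
2. State that the threshold of 2 per degree of freedom refers to a reduction in AIC (LR > 4 for one added predictor).
3. Add that AIC is compared only between models fitted to the same subjects and the same response variables.

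In the Aim 2 analysis text of Section 11.0, refer to the same definition, and state that where a response is transformed, AIC is compared on a common scale with the Jacobian term included.

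The cost is a few sentences. No data, patients, visits or sample-size figures change.
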